14.2 Imaging Science Studies in Alliance A021501: Alliance A021501-IM1

We propose three imaging correlates for this study. The primary objective of these correlative studies is to prospectively validate prognostic biomarkers derived from imaging. We have reviewed how previous clinical trials in this disease could have benefited from stratification and proper selection [45] [46]. By validating the imaging-based biomarkers in this trial, we can develop a better understanding of the results of this trial and design the next generation of trials with these biomarkers in mind. We have previously shown that standard imaging can correlate with drug delivery in PDAC [36]. Our group has pilot data to suggest that two imaging-based properties independently predict overall survival (OS) outcomes of patients. These measurements are the degree of enhancement in the tumor relative to the normal pancreas (called normalized area under the enhancement curve, NAUC) and a measurement of the morphology of the tumor (called the delta measurement). Our pilot data also indicate that changes in NAUC associate with local control of the tumor, and we hypothesize this observation is due to the

pathological response in the tumor after neoadjuvant therapy. With a planned accrual of 134 patients in this Alliance trial, we will be well powered to prospectively validate our pilot data.

14.2.1 Primary Objectives

To evaluate risk classification previously developed by Koay et al. [36] using NAUC.

To assess prognostic value of NAUC ratio defined as post-neoadjuvant NAUC divided by pre-neoadjuvant therapy NAUC.

To evaluate risk classification previously developed by Koay et al. using delta measure.

14.2.2 NAUC and OS

In a pilot study of 110 patients who underwent neoadjuvant gemcitabine-based chemoradiation for resectable pancreatic cancer, NAUC from pre-therapy CT scans associated with OS as a survival variable. Exploratory analysis (Koay et al, JCI 2014) identified a cutoff of 0.6 for NAUC, differentiating patients into two prognostic groups: high NAUC (20% of patients) and low NAUC (80% of patients) [36]. The hazard ratio for this cutoff was 0.46 [0.24, 0.79], favoring patients with a higher NAUC.

To validate the cutoff, NAUC will be calculated for each evaluable patient based on pre-therapy CT scans. Patients will then be categorized into two groups based on NAUC value (> 0.6 versus ≤ 0.6). Proportional hazard model will be used to examine the associate between NAUC grouping (high versus low) and overall survival adjusting for treatment arm to assess the prognostic value of NAUC.

Assuming 20% of patients will have NAUC > 0.6 , we will have 80% power to detect a difference in overall survival at a one-sided 5% significance level with a hazard ratio of 0.47. The power curve for different percentages of patients who have NACU > 0.6 is shown in Figure 4 below. This power analysis assumes an accrual period of 31 months, a minimum follow up of 20 months, an accrual rate of 4 patients per month, and median survival in the worst group of 18 months.

[figure not shown]

Figure 4. Power curve for different percentages of patients who have NAUC > 0.6 .

NAUC will be calculated for each evaluable patient based on pre-therapy CT scans. Patients then will be categorized into 2 groups based on NAUC value (> 0.6 vs. ≤ 0.6). Proportional hazard model will be used to examine the association between NAUC grouping and overall survival

If NAUC > 0.6 cutoff is not validated, we will explore an additional cut-point to better differentiate patients to two risk groups. The methods used for exploratory analysis including, but not limited to, 1) graphical approaches based on Martingale Residual plot [47], 2) Mazumdar and Classman cut-off identification strategy [48] (minimum p-value and maximum HR approach), and 3) Contal and O'Quidley method (changepoint method) [49]. A detailed analysis plan will be formulated prior to actual data analysis.

14.2.3 Changes in NAUC and Pathological Response.

As a second correlate for the mass transport properties, the change in NAUC during therapy may also provide important information. As an exploratory exercise, NAUC will be calculated for each evaluable patient based on pre-therapy and pre-surgery CT scans. A NAUC ratio of pre-surgery to pre-therapy NAUC will then be calculated for each patient. Proportional hazard model will be used to examine the association between NAUC ratio grouping, progression free survival and overall survival

Additionally, we propose analyzing changes in the NAUC (comparing post-neoadjuvant therapy and pre-neoadjuvant therapy) as a prognostic biomarker of the pathological response to neoadjuvant therapy. Our pilot data indicate that patients who have a decrease in NAUC after neoadjuvant therapy (NAUC ratio of post- to pre- NAUC less than 1) have significantly better local control than those who have a NAUC ratio above 1, with a hazard ratio of 3.01 [1.45, 6.25]). We hypothesize this difference in the groups is based on response at the pathological level. As an exploratory study, we will score the pathological response in patients who undergo resection on this Alliance trial and measure NAUC on post- and pre-therapy CT scans, similar to our previously published methods.[36] This estimate was based on a conservative estimate of the hazard ratio from our pilot study (2.2) and the same assumptions as (A). The model will include a treatment arm indicator. In addition, the predictive value will be assessed by testing the interaction between NAUC and treatment arm.

If our preliminary data reflect the differences that we can expect, then we estimate we will need a minimum of 62 patients to detect a difference in the NAUC ratio between those who have an excellent response to therapy from all others. This estimate was based on a conservative estimate of the hazard ratio from our pilot study (2.2) and the same assumptions as (A).

NAUC ratio of pre-surgery to pre-therapy NAUC will be calculated for each patient. Proportional hazard model will be used to examine the association between NAUC ratio (as a continuous variable) and overall survival adjusting for treatment arm to assess the prognostic value of NAUC ratio. Optimal cut point of NAUC ratio will be explored to dichotomize patients into two risk groups.

Assuming 60% of evaluable patients (N=74) undergo resection, there will be 41 events. The power curve is a function of hazard ratio and the variance of the NAUC ratio (Figure 5).

[figure not shown]

Figure 5. Power curve as a function of hazard ratio and the variance of the NAUC ratio.

We will have 80% power to detect a difference in overall survival at a two-sided 5% significance level with a hazard ratio of 1.55 if the variance of NAUC ratio is one. Similarly, we can detect a difference of 1.32 and 2.4 if the variance of NAUC ratio is 1.5 and 0.5, respectively. This power analysis assumes a minimal follow-up of 20 months and accrual rate of 4 patients per month. A detailed analysis plan will be formulated prior to actual data analysis.

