6.4.2 CT Submission Instructions

The following images and local interpretation reports will be collected digitally and submitted for centralized, **real-time re-review** (in addition for the A021501-IM1 correlative study and for banking purposes):

- Baseline (within 28 days prior to patient registration): This scan will be reviewed centrally to ensure that patient meets the criteria for borderline resectable disease, as detailed in [Section 3.2.1](#) and [Appendix II](#).
- Pre-Surgery Restaging:
 - i) Arm 1 (after 8 cycles of mFOLFIRINOX and prior to surgery).
 - ii) Arm 2 (after 7 Cycles of mFOLFIRINOX + Radiotherapy and prior to surgery)

This scan will be reviewed centrally to determine if the patient has potentially resectable disease and is appropriate for surgical intervention, at completion of preoperative therapy.

For patients who consent to the imaging study A021501-IM1 (model consent question, “I agree to have my scan images be collected and submitted for the research stated above”), the following scans and local interpretation reports should also be submitted to the IROC Ohio Imaging Core Lab (ICL) for the A021501-IM1 correlative study and banking purposes. These scans may be batched shipped every 6 months:

- Post 4 cycles of mFOLFIRINOX (See [Section 5.0](#))
- Post-surgery restaging (Post-Surgery and prior to first cycle of FOLFOX)
- Post 4 Cycles of FOLFOX
- Post-Treatment Follow-Ups (every 16 weeks +/- 28 days after completion of treatment for 24 months post-registration or until documented progression, whichever occurs first)

All scans must be submitted digitally. CD/DVD shipment of images is **not** allowed.

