If delta measure > 40 HU is not validated, we will explore an additional cut-point to better differentiate patients into two risk groups. The methods used for exploratory analysis include, but are not limited to, the following: 1) graphical approaches based on Martingale Residual plot [47] 2) Mazumdar and Classman cut-off identification strategy [48] (minimum p-value and maximum HR approach), and 3) Contal and O'Quidley method (changepoint method) [49]. A detailed analysis plan will be formulated prior to actual data analysis.

The delta measurement will be calculated for each evaluable patients based on pre-therapy CT scans. We will examine measurement and search for a cut-point which will separate patients into two distinct prognostic groups. Proportional hazard model will be used to examine the association between delta measurement grouping and overall survival.

The delta measurement will be calculated for each evaluable patient based on pre-therapy CT scans. Proportional hazard models will be used to examine the association between delta measurement grouping and overall survival adjusting for treatment arm. In addition, the predictive value will be assessed by testing the interaction between the delta variable and treatment arm. We will examine the delta measurement and outcome, and evaluate the possibility of search for a cut-point which may separate patients into two distinct prognostic groups.

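### Section 14.2.3 calls a NAUC-by-arm interaction predictive, but NAUC change is measured after the randomized preoperative treatment, so the test cannot show who benefits from which arm

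*Combined protocol and SAP*

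**What the plan says.** Section 14.2.3 is motivated by the idea that "the change in NAUC during therapy may also provide important information". It defines the marker from two scans: "A NAUC ratio of pre-surgery to pre-therapy NAUC will then be calculated for each patient". Its second paragraph proposes NAUC change as a biomarker of pathological response in patients who undergo resection, adds an arm indicator to the model, and ends: "In addition, the predictive value will be assessed by testing the interaction between NAUC and treatment arm".

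Section 6.4.2 fixes when the second scan is taken: "Arm 1 (after 8 cycles of mFOLFIRINOX and prior to surgery", and "Arm 2 (after 7 Cycles of mFOLFIRINOX + Radiotherapy and prior to surgery".

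Three other places bear on the point:

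- Section 14.2.1 lists only a prognostic aim for the ratio: "To assess prognostic value of NAUC ratio defined as post-neoadjuvant NAUC divided by pre-neoadjuvant therapy NAUC".
- Section 14.2.2, on pre-therapy NAUC, plans a main effect with no interaction: "Proportional hazard model will be used to examine the associate between NAUC grouping (high versus low) and overall survival adjusting for treatment arm".
- Section 14.2.4, on the delta measure from the pre-therapy CT, does plan one: "the predictive value will be assessed by testing the interaction between the delta variable and treatment arm".

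Section 14.2.3 calls the pathological-response work exploratory and defers details to a later analysis plan. Section 7.0 records that Arm 2 closed to enrollment, and that Arm 2 treatment of enrolled patients stopped, on 08/13/2018.

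**The concern.** A predictive marker has to be available when treatment is chosen and must not itself be a product of that treatment. The NAUC ratio fails on both counts: it does not exist until the randomized preoperative treatment is over. Section 14.2.3 itself supposes that NAUC change reflects pathological response, which makes it a readout of treatment effect.

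Restricting to resected patients adds a second selection after randomization. Section 13.2 expects 40% of randomized patients to be off protocol treatment before surgery.

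What is at stake is the reading of a significant result. Labelled as planned, it would invite the claim that NAUC indicates which regimen suits which patient, in a substudy that section 14.2 says should inform the design of later trials.

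**Working it through.** **1. The three imaging markers side by side**

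| Marker | When it is read | Interaction with arm planned? |
|---|---|---|
| Pre-therapy NAUC (14.2.2) | Before treatment | No, arm adjustment only |
| NAUC ratio (14.2.3) | Second scan after all randomized preoperative treatment (6.4.2) | Yes, on the natural reading |
| Delta (14.2.4) | Before treatment | Yes |

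**2. What the interaction estimates**

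Let A be the arm, M0 a baseline marker and M(A) the ratio that a patient would have under arm A.

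- With M0, patients with M0 = m in the two arms are exchangeable by randomization. An interaction describes how the arm effect varies with m.
- With the ratio, the test compares Arm 2 patients with M(2) = m against Arm 1 patients with M(1) = m. These are different kinds of patient whenever treatment moves the ratio.

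The second comparison is unprotected by randomization however large or small any radiation effect is.

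**3. The plan's power figure**

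Section 14.2.3 gives 74 resected patients (0.60 × 124 = 74.4), 41 events, two-sided 5%, 80% power, and hazard ratio (HR) 1.55 at variance 1. The events needed are (1.960 + 0.842)² / (1 × (ln 1.55)²) = 7.849 / 0.1921 = 40.9. The figure reproduces, but it is for the prognostic main effect. No power is given for the interaction.

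**4. Power of an interaction with the same events**

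For a continuous marker with SD 1, SE = √(1/d1 + 1/d2), where d1 and d2 are the events per arm.

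- 41 events split equally: SE = √(2/20.5) = 0.312. The detectable ratio of HRs is exp(2.802 × 0.312) = 2.40. Power for a ratio of 1.55 is Φ(0.438/0.312 − 1.960) = 29%.
- 30 evaluable Arm 2 patients (assumed; no count is given): about 20.6 and 10.0 events, detectable ratio 2.95.
- 15 evaluable Arm 2 patients (assumed): about 20.6 and 5.0 events, detectable ratio 4.05.

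**5. Illustration: can a slope difference arise when no patient is better suited to either arm?**

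The setting is a Cox model for OS with 74 patients allocated 1:1, exponential survival with median 27 months, uniform censoring at 20 to 51 months, and 1,500 runs per row. The arm HR is 1 for every patient. An underlying prognostic factor has HR 1.55 or 2.2 per SD. The rows are assumptions about Arm 2; none comes from the documents. Entries are rejection rates of a nominal 5% interaction test on a continuous marker.

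| Marker behaviour in Arm 2 | HR 1.55 | HR 2.2 |
|---|---|---|
| Baseline marker | 6.4% | 6.1% |
| Ratio unaffected by radiation | 5.8% | 6.5% |
| Ratio shifted equally in all | 6.2% | 4.9% |
| Correlation with prognosis cut to 0.5 | 11.1% | 26.0% |
| Spread compressed to 0.4 | 18.9% | 45.9% |
| Link to prognosis lost | 28.1% | 64.5% |

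The Monte Carlo standard error near 5% is √(0.05 × 0.95/1500) = 0.6 points. With 124 patients the last three rows become 17.7/38.9%, 28.3/69.7% and 43.5/86.4%.

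A uniform shift does no harm to the test. Radiation would have to change the spread of the ratio or its link to prognosis. In those rows the slopes really do differ by arm, so the test is not malfunctioning; the error lies in reading the difference as treatment selection.

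**The case against.** **The variable is ambiguous.** The sentence says NAUC, not NAUC ratio, and 14.2.2 uses the bare term for the pre-therapy value. The paragraph also looks disordered: it explains the basis of an estimate before giving one, repeats that explanation in the next paragraph, and refers to an undefined item (A). This stands. The paragraph's subject favors the change reading but does not settle it. A reader might infer that the baseline question has been left untested; the text does not establish that.

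**The magnitude is assumption-driven.** A reader might infer that the test will give false positives at some known rate. The documents do not support this: they nowhere say that radiation alters NAUC, and the rates depend on how strongly the ratio tracks tumor biology. In a logistic version (37 per arm), tripling the Arm 2 residual SD gave rejection of 25–45% or 12–21%, depending only on that assumed strength. With 10 resected Arm 2 patients (assumed), rejection was 12–16% without added radiation noise and 12–17% with the largest amount, so there the excess comes from sparse data.

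**The interaction has a legitimate use.** The ratio model adjusts for arm and so assumes one slope for both arms; the interaction checks that. This stands, so outright deletion is not required.

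**The work is exploratory, and a detailed plan will follow.** True, and it limits the impact. But the current text contains nothing, such as a causal method for a post-treatment marker or a caution, that would lead the later plan to correct the label.

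**A baseline NAUC-by-arm test would be weak.** With 20% high NAUC, full accrual gives 0.20 × 124 ≈ 25 such patients, about 12 per arm, and fewer in Arm 2 after its closure. This stands and belongs in the label.

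**Conclusion.** As written, and on the natural reading that the sentence concerns NAUC change, the predictive label is wrong. The marker follows the randomized preoperative treatment, and pathological response is observed only in a treatment-selected set. This conclusion rests on sections 6.4.2 and 14.2.3 alone and needs no assumption about radiation. If pre-therapy NAUC was intended, the test is valid in principle but is attached to the wrong section and patient set.

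Radiation altering the marker is a possible cause of a slope difference, not a documented one, and no rate of misleading results can be fixed from the documents. Power is low in any case: a ratio of HRs of 2.40 per SD would be needed under full accrual, and more with fewer Arm 2 events. Because Arm 2 treatment was stopped, some Arm 2 patients may also have had no radiation before the second scan.

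The impact is limited to an exploratory correlative analysis. No primary or secondary endpoint of the trial and no arm decision depends on it.

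**What to change.** - **Section 14.2.3.** State that NAUC change is assessed as prognostic or response-related only. Either remove the interaction with arm, or keep it solely as a check that the prognostic slope is common to both arms, with no predictive claim.
- **Section 14.2.2.** Move the NAUC-by-arm test here, using pre-therapy NAUC in the Cox model for OS, in concurrently randomized evaluable patients with a baseline CT. This matches the treatment of delta in 14.2.4. Label it exploratory and low-powered because Arm 2 closed early.
- **General rule for 14.2.** Reserve predictive interaction tests for pre-therapy markers, and name the variable in each sentence (pre-therapy NAUC or NAUC ratio).

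The cost is a few sentences of plan wording. Baseline scans are already collected, so no new data are needed. What is given up is one predictive claim that the design cannot support; the slope check can be kept.

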Fisher's Exact test will be used to assess the association of the GG genotype with worse 18 month OS. With a total sample size of $N=125$ in both arms, and 85% expected rate of consent to this study, we expect a sample size of 106 for this aim. We assume 63% 18 month OS rate (the alternative hypothesis in the primary aim of this trial) and 16% prevalence of the GG variant. We expect $n=17$ GG variant patients. Under these assumptions, a Fisher's Exact test has 82% power to detect a difference of 44% versus 82% (i.e. a delta of 38%) 18 month OS rates between the groups defined by the GG variant. Nonparametric methods such as recursive partitioning for classification, regression and survival trees (RPART) will be used to explore a possible predictive value of the GG genotype (secondary objective 1), and prognostic value of common variants (secondary objective 2) [44]. In secondary objective 4, generalized linear model methods and penalized regression together with cross validation will be used to evaluate the association between germline variation and molecular markers of inflammation, immunity, angiogenesis, and stromal functions in an exploratory fashion.

Similar approaches to *Quality Control and Normalization of Expression Data, Differential expression, Model Building, and Internal Model Validation* will be employed. We will stay abreast of the literature for methods that are appropriate for data analysis. A detailed analysis plan will be formulated prior to actual data analysis.

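### Two substudy power statements need a minor correction: the detectable NAUC-ratio hazard ratios at variance 1.5 and 0.5, and a VDR alternative (44% vs 82%) that cannot average to the assumed 63% survival

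*Combined protocol and SAP*

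**What the plan says.** **NAUC ratio (imaging substudy A021501-IM1, section 14.2.3).** The analysis is a proportional hazards model for the "association between NAUC ratio (as a continuous variable) and overall survival", adjusted for treatment arm. The event count is given as: "Assuming 60% of evaluable patients (N=74) undergo resection, there will be 41 events". Power is 80% at two-sided 5%, "with a hazard ratio of 1.55 if the variance of NAUC ratio is one". The section then extends this to two other spreads of the covariate: "Similarly, we can detect a difference of 1.32 and 2.4 if the variance of NAUC ratio is 1.5 and 0.5, respectively". It refers to Figure 5 for the power curves.

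**VDR variant (pharmacogenetic substudy A021501-PP1, section 14.1.3).** The planned sample is 106, which is 85% consent applied to 125 patients in both arms. The assumptions are: "We assume 63% 18 month OS rate (the alternative hypothesis in the primary aim of this trial) and 16% prevalence of the GG variant". The section continues: "We expect $n=17$ GG variant patients". On that basis a Fisher's exact "test has 82% power to detect a difference of 44% versus 82" percent, described as a difference of 38 points. Section 14.1.2 gives the direction: GG is expected to do worse. Section 14.1.3 states neither the significance level nor the sidedness for this test.

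**The concern.** In the usual formula for a continuous covariate in a Cox model, the detectable log hazard ratio is proportional to 1/sqrt(variance). The three hazard ratios in section 14.2.3 do not follow that scaling, so they cannot all be right as labelled. The two errors run in opposite directions: 1.32 makes the study look more sensitive than it is, and 2.4 makes it look less sensitive.

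In section 14.1.3, 84% of patients are placed at 82% survival and the remaining 16% at 44%, while overall survival is assumed to be 63%. A weighted average dominated by 82% cannot come down to 63%.

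At stake are the stated operating characteristics of two embedded substudies. No sample size, decision rule or conduct of the main trial depends on them.

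**Working it through.** **1. NAUC ratio**

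Inputs, all from section 14.2.3: D = 41 events; continuous covariate; two-sided 5% (z = 1.960); 80% power (z = 0.842). The sum of the z-values is 2.8016.

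Formula: HR = exp(2.8016 / sqrt(D × variance)).

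The plan's anchor at variance 1: exp(2.8016 / sqrt(41)) = exp(0.4375) = 1.549. This reproduces the stated 1.55.

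The other two values:

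| Spread as labelled | Stated HR | HR if a variance | Power of stated HR if a variance | HR if an SD |
|---|---|---|---|---|
| 1 | 1.55 | 1.549 | 80% | 1.549 |
| 1.5 | 1.32 | exp(2.8016/sqrt(61.5)) = 1.429 | 59% | 1.339 |
| 0.5 | 2.4 | exp(2.8016/sqrt(20.5)) = 1.857 | 98% | 2.399 |

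Power is Phi(sqrt(D × variance) × ln HR − 1.960). For 1.32: Phi(7.842 × 0.2776 − 1.960) = Phi(0.217) = 0.586. For 2.4: Phi(4.528 × 0.8755 − 1.960) = Phi(2.004) = 0.977.

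Events needed for 80% power are 2.8016² / (variance × (ln HR)²): about 68 for 1.32 at variance 1.5, and about 21 for 2.4 at variance 0.5.

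A Cox-model simulation (74 patients, 41 events, normal covariate, exponential survival, 6,000 runs, two-sided 5% Wald test) gave 58% for 1.32 at variance 1.5 and 96% for 2.4 at variance 0.5. It gave 77% to 78% for 1.55, 1.43 and 1.86 at variances 1, 1.5 and 0.5.

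A check that does not need the event count, alpha or power:
- From variance 1 to 0.5, ln HR must rise by sqrt(2) = 1.41. The stated values give ln 2.4 / ln 1.55 = 0.8755 / 0.4383 = 2.00.
- From variance 1.5 to 1, ln HR must rise by sqrt(1.5) = 1.22. The stated values give 0.4383 / 0.2776 = 1.58.

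So no choice of events, alpha or power reconciles the three values as variances. A factor of 2.00 is what an SD of 0.5 produces.

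**2. VDR variant**

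Inputs from section 14.1.3: 106 patients, 16% GG (17 GG, 89 others), 63% overall survival, 44% in GG, 82% in the rest.

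- Implied overall survival: 0.16 × 0.44 + 0.84 × 0.82 = 0.0704 + 0.6888 = 0.759.
- Floor set by the non-GG patients alone: 0.84 × 0.82 = 0.689, even if every GG patient dies before 18 months.
- GG survival needed to reach 63%: (0.63 − 0.6888) / 0.16 = −0.37, which is impossible.
- Unweighted midpoint: (0.44 + 0.82) / 2 = 0.63. The pair fits 63% only at 50% GG prevalence.

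A 38-point pair that does average 63%: rest = 0.63 + 0.16 × 0.38 = 0.691; GG = 0.63 − 0.84 × 0.38 = 0.311.

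Fisher's exact power by full enumeration, 17 versus 89:

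| Test level | 44% vs 82% | 31.1% vs 69.1% |
|---|---|---|
| One-sided 2.5% | 82.9% | 77.0% |
| Two-sided 5% | 86.1% | 80.4% |
| One-sided 5% | 88.7% | 86.4% |

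Of these levels, one-sided 2.5% comes closest to the stated 82%. The power arithmetic for the stated pair is therefore reproducible; the fault lies in the pair of rates and the unnamed test level.

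**The case against.** The strongest reply is that little turns on either statement. Substudy size is set by the parent trial and no decision rule uses these figures. Section 14.2.3 describes part of the NAUC-ratio work as exploratory, and both sections defer to a detailed analysis plan before analysis. The likely cause in 14.2.3 is a label: an SD of 0.5 gives 2.40 and an SD of 1.5 gives 1.34, close to 1.32. All of that stands as an argument on weight, and this is accordingly a minor correction. It does not make the sentences right. The SD reading is itself an inference: 1.32 fits only approximately (76% power at SD 1.5), and Figure 5 was not available to check.

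Three stronger readings are tempting and are not supported.

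- A reader might infer that VDR power collapses once the rates are made consistent, by keeping GG at 44% and overall survival at 63%. The rest would then be at (0.63 − 0.0704) / 0.84 = 67%, a difference of about 23 points. Section 14.1.3 specifies 38 points, so power for 23 points says nothing about the stated alternative.
- A reader might infer that a consistent pair necessarily falls short of the stated 82%. That depends on the unstated test level. Section 14.1.2 gives a directional hypothesis and section 14.2.2 uses one-sided 5%, so one-sided 5% is a possible reading, and there the consistent pair has 86%.
- A reader might infer that the remaining imaging power statements, in 14.2.2 and 14.2.4, have been cleared. They have not. An approximate check of 14.2.2 (about 84 events, 20% high NAUC, HR 0.47, one-sided 5%) gives Phi(sqrt(84 × 0.16) × 0.755 − 1.645), or about 87% against the stated 80%. That gap is conservative and may reflect another method.

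**Conclusion.** Both statements are wrong as written, and the consequence is minor.

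In section 14.2.3 the detectable hazard ratios are 1.43 and 1.86, not 1.32 and 2.4, if the spreads are variances. This rests on the stated 41 events and the standard formula that reproduces the plan's own 1.55; the scaling argument does not even need the event count.

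In section 14.1.3 the pair implies 76% overall survival, 13 points above the assumed 63%, and no GG survival rate can rescue it. Restoring consistency at the same 38-point difference lowers power by about 6 points at one-sided 2.5% or two-sided 5%, and by about 2 points at one-sided 5%.

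All these figures take the planned two-arm numbers as given (74 resected patients with 41 events; 106 consenting patients). Sections 7.0 and 13.0 record that Arm 2 closed to enrolment on 08/13/2018, so the corrected figures repair the algebra and do not describe what the substudies can now attain.

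**What to change.** In section 14.2.3, replace 1.32 and 2.4 with 1.43 and 1.86. If standard deviations were intended, change variance to SD in that sentence and state 1.34 and 2.40. Check Figure 5 against whichever is chosen.

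In section 14.1.3, replace 44% versus 82% with a 38-point pair that averages 63% at 16% GG, about 31% versus 69%. Name the alpha and sidedness and state the matching Fisher power for 17 versus 89: 77% at one-sided 2.5%, 80% at two-sided 5%, or 86% at one-sided 5%.

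Add a line to both sections that the figures assume the original two-arm accrual, and let the detailed analysis plans promised there restate them for the patients actually available.

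The cost is a few sentences, with no change to sample size, primary design or conduct.
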